NCT02522429

**Thalamic Low Intensity Focused Ultrasound in Brain
Injury**

10/30/2020

Background

Few neurological conditions are as scientifically mysterious and clinically, legally, and ethically challenging as disorders of consciousness (DOC)¹. Typically developed after severe brain injury, this set of related conditions includes Coma, the Vegetative State (VS) and the Minimally Conscious State (MCS)². In the past 20 years, an increasing amount of research has broken many conventions about these disorders, including the once widespread belief that these patients are entirely *apallic* – that is, lack any kind of “higher” activity³. Since then, it has been shown that a lot of brain activity, including relatively high-level cognitive processes, can remain in DOC patients. Nonetheless, to date there exists no standard intervention for patients suffering from these devastating conditions. Developing interventions for this population is extremely important first and foremost for the well-being of patients, who – today – remain completely dependent on assisted care, are often unable to participate in rehabilitative programs because of their lack of behavioral responsiveness, and thus find themselves prisoners of a condition characterized by uncertainty at the medical, legal and ethical decision-making levels⁴. In addition, these conditions, which can last indefinitely, also place great emotional and monetary strain on families, large burdens on care-takers – often leading to increased rates of burn-out⁵ – and large financial stress on medical structures and public finances due to the large costs imposed by prolonged intensive care.

The present project is aimed at evaluating the potential of non-invasive Low Intensity Focused Ultrasound Pulsation (LIFUP) of thalamus as a neuro-restorative stimulation for patients with severe brain injury.

The **rationale** for this proposal hinges upon four premises:

- (i) To date, there exists **no standard intervention** for severe brain injury patients who develop disorders of consciousness
- (ii) Recent advances in our understanding of the physiological mechanisms accompanying the loss and recovery of consciousness and cognitive function after severe brain injury suggest **specific neural targets for therapeutic intervention**⁶⁻⁸
- (iii) Invasive surgical techniques based on permanently implanting neurostimulating electrodes in the brain (i.e., Deep Brain Stimulation – DBS) have shown that **thalamic stimulation can lead to behavioral improvements in patients with severe brain injury**⁹⁻¹³
- (iv) Low-Intensity Focused Ultrasound Pulsation (LIFUP) stimulation¹⁴ has been shown to be an **effective and safe neuromodulation technique** in humans¹⁵, consistent with data from animal models, including rodents¹⁶ and non-human primates¹⁷. The empirical safety data is also well justified from a theoretical point of view considering that LIFUP delivers stimulation of intensities **below** those of commonly used ultrasound applications (e.g., pre-natal ultrasonography, doppler ultrasounds), as well other neuromodulatory techniques (e.g., Transcranial Magnetic Stimulation – TMS)

In this project, we propose to assess, in a small number of patients with severe-TBI, the feasibility of LIFUP as a non-invasive alternative to stimulation via neuro-surgical insertion of brain electrodes (i.e., DBS). More specifically, we have three main aims:

Aim 1: Assess the feasibility and preliminary efficacy of LIFUP thalamic stimulation, as measured by changes in clinical assessments measures of consciousness and behavioral responsiveness.

Aim 2: Assess the brain effects of LIFUP stimulation, as measured by functional MRI and the degree to which they correlate with clinical/behavioral changes.

The **main hypotheses** underlying the project are:

H1: As shown by previous literature¹⁵⁻¹⁸, LIFUP stimulation is a safe and effective neuro-modulatory technique.

H2: LIFUP thalamic stimulation is associated with an increase in clinical measures of patient arousal and/or awareness to an extent at least comparable to that demonstrated with neurosurgical thalamic stimulation procedures (i.e., DBS)⁹⁻¹³.

H3: The neuro-restorative effects of LIFUP stimulation are associated with detectable changes in brain function as detected with fMRI.

Protocol

The **research strategy** is to recruit patients who have suffered a severe TBI and are in a Disorder of Consciousness (18 years or older and no contraindications to entering the MRI environment). Patients will be recruited either as Acute DOC patients or Chronic DOC patients.

Inclusion Criteria:

Acute patients

< 6 weeks since injury

A Glasgow Coma Score < 9 (at the time of injury)

Abnormal CT

Prolonged loss of consciousness (>24h)

Behavioral profile consistent with a VS or MCS as assessed with the Coma Recovery Scale Revised.

Chronic patients

> 3 months post injury for non-traumatic injuries, >12 months post-injury for traumatic injuries

Behavioral profile consistent with a VS or MCS as assessed with the Coma Recovery Scale Revised.

Exclusion Criteria (all patients):

deep sedation

history of neurological illness prior to injury

inability to safely enter the MR environment (e.g., ferromagnetic non MR safe implants)

Neurobehavioral Assessment Procedure

Neurobehavioral assessments will be conducted using the Coma Recovery Scale Revised (CRS-R).¹⁹ Baseline responsiveness will be assessed prior to LIFUP exposure. Responsiveness will also be assessed immediately following, as well as on the days following each LIFUP exposure. The Coma Recovery Scale – Revised, is a standard clinical protocol used to assess a patient's level of consciousness. This test allows us to assess your level of response to sensory stimulation, ability to understand language and to communicate. This procedure is typically administered at bedside. This testing should take 25 minutes.

In addition, the Glasgow Outcome Scale extended score will be assessed to evaluate outcome at protocol end and follow-up

Paramedical Measurements

- (1) Clinical EEG: data from the clinical recordings will be collected.
- (2) MR acquisition (performed in MR suite):
 - (A) Structural MRI acquisition:
 - (i) T1-weighted (MPRAGE)
 - (ii) Diffusion Tensor Imaging (DTI)
 - (B) Functional MRI acquisition:
 - (ii) Resting state task (BOLD, during sonication)

Electroencephalography (EEG) is a widely employed technique that measures electrical brain activity. In order to acquire EEG data we will fit you with a small elastic cap that you will wear on your head. This procedure (expected duration: 10 minutes + set-up time, up to 20 minutes) will allow us to measure electrical brain activity as you rest. This procedure is entirely non-invasive.

Magnetic Resonance Imaging (MRI) is a widely used method to assess body tissues, including the brain, in a non-invasive manner. In the context of this study, MRI will be used to assess brain structure and function (in response to LIFU). MRI protocols include T1 MPRAGE, Diffusion Tensor Imaging (DTI), and T2* BOLD sequences.

Procedure

The temporal sequence of events, for each cycle, is as follows:

- Clinical EEG (baseline): 10 min of EEG data, from the clinical recordings, will be collected for analysis
- Baseline clinical measures collection (25 min)
- Baseline fMRI measures collection (in MRI suite; 30 min+20 min set-up)
- Administration of LIFUP (in MRI suite; 10 min + 20 min set-up)
- Post-LIFUP fMRI measures collection (in MRI suite; 30 min)
- Post-LIFUP clinical measures collection (25 min)
- Clinical EEG (post-LIFUP): 10 min of EEG data, from the clinical recordings, will be collected for analysis

LIFU Procedure. The area surrounding the planned LIFU entry point on the head will be shaved prior to positioning in order to minimize the impedance of ultrasound due to air bubbles. Ultrasound gel (aquasonic) will be first applied to this region and smoothed in order to remove air pockets. The ultrasound transducer will then be positioned so that its center lay on the squamous portion of the temporal bone (the thinnest part of the human skull) in order to minimize ultrasound scatter and refraction through the bone. A thin layer of gel will be applied to the surface of the transducer, and bubbles will be similarly smoothed from this layer. The transducer will then be coupled to the head with gel filling any open space between the transducer membrane and the scalp with two straps—one horizontal and one vertical—securing the device to the patient. Conventional soft foam padding and pillows will be used to further secure the positioning of the device and decrease the potential for head motion during the procedure. Next, we will acquire a rapid (95 s) T1-weighted MPRAGE anatomical image. Using a circular MR fiducial and the visible center of the transducer, reference lines will be drawn in the transverse and coronal planes, using the Siemens 3D display GUI available as part of the MRI device's console software to visually locate the target of the LIFU beam

in three dimensions. Adjustments to the positioning of the transducer on the head will be made iteratively, re-acquiring a T1-weighted MPRAGE at each iteration, until the beam trajectory from the center of the transducer is assessed to be in-line with the intended target.

Statistical Plan and Analysis

- **Change in CRS-R related to LIFUP.** *Maximum CRS-R score prior to LIFUP will be compared to the maximum CRS-R score following LIFUP.* Behavioral responsiveness in patients was assessed using the total score on the CRS-R. Prior to analysis, the highest CRS-R prior-to and following LIFUP exposure will be calculated in order to best capture patients' maximal performance. A matched samples T-test analysis will be performed. Where a violation of normality is detected (using a Shapiro-Wilk test) a non-parametric Wilcoxon signed rank test will be used to compare Pre-LIFUP and Post-LIFUP scores for all patients.
- **Change in BOLD signal during LIFUP.** *Brain BOLD signal during exposure to LIFUP will be compared to the brain BOLD signal during inter-stimulation intervals.* MRI data preprocessing and analysis will be conducted using FSL (FMRIB Software Library v6.0.1) with in-house Bash shell scripts. Preprocessing will include brain extraction (using optiBET), spatial smoothing (using a Gaussian kernel of 5 mm full-width half-max), slice timing correction (Fourier-space time-series phase-shifting), highpass temporal filtering (Gaussian-weighted) at 0.01 Hz, and motion correction (MCFLIRT). With the exception of brain extraction, these procedures will be performed in fsl FEAT. Following recent data, in-scanner head motion will be mitigated by including in the statistical model a number of nuisance regressors, including individual time points with excessive motion (i.e., spike regression) derived from the output of fsl FLIRT, head-motion parameters, and regressors for white matter and CSF components. White matter and CSF regressors will be produced by segmenting T1 images for each patient using FSL Fast (visually inspected for accuracy). Tissue segmentations for white matter and CSF will be transformed into functional space and binarized (and again visually inspected for accuracy). Time series for white matter and CSF will then be extracted from functional images using fslmeans. Framewise displacements for each volume will be derived from FSL MCFLIRT and used to exclude unwanted volumes with a framewise displacement exceeding 0.5 mm (25% of voxel width). In order to register structural images to functional space, we will employ a combination of FSL epi_reg and conventional 12 dof linear coregistration (using FSL FLIRT). In order to register structural images to standard space, nonlinear registration (FSL FNIRT) will be used. BOLD data collected during LIFUP will first be analyzed employing a univariate general linear model (GLM) approach, including pre-whitening correction for autocorrelation (FILM). A univariate analysis will be conducted using a single "task" regressor, which represents the onset time of 30 s blocks of LIFUP administration. Thus, here the "baseline" conditions used will be the inter-sonication periods where no LIFUP is applied. For each BOLD sequence, we will compute the contrast LIFUP > Rest. For patients with two LIFU exposures, results from the two runs will be averaged at level two prior to third-level analysis. At the third level, data will be cluster corrected for multiple comparisons using a familywise cluster correction ($p < 0.05$).
- **Structural MRI – Diffusion Tensor Imaging (DTI).** The aim of this analysis is to assess any changes, in terms of structural connectivity, and in particular thalamo-frontal connectivity, induced

by the LIFUP stimulation. Data will be first preprocessed following standard pipelines in the field (Behrens et al., 2003b); then, streamlines from thalamus to the whole brain will be calculated, for every subject individually, between thalamus and cortex (Behrens et al., 2003a). The streamlines will then be entered, the dependent variable, in the group analysis (i.e., the mixed-design ANCOVA). This analysis is a direct test of whether thalamo-cortical connectivity is affected (as the mesocircuit hypothesis predicts) by our intervention.

- **Electroencephalography.** This analysis is aimed at assessing whether LIFUP session alters the spectral profile of electroencephalographic recordings (EEG). Indeed, it is known that patients at different levels of consciousness after severe brain injury exhibit different electrocortical patterns (e.g., patients with severe disorder of consciousness exhibit large "delta" -- that is: slow -- waves of activity, as compared to the more rapid "alpha" waves typically seen in healthy individuals). Data will be preprocessed following previous literature (Lechinger et al., 2013), then for each channel we will derive a characterization of each patient's spectral profile. This information will then be entered in the group analysis.

1. Monti MM. Ethics, Neuroimaging and Disorders of Consciousness: What Is the Question? *AJOB Neuroscience*. 2013;4(4):1-2.
3. Monti MM. Cognition in the vegetative state. *Annu Rev Clin Psychol*. 2012;8:431-54. Epub 2012/01/10. doi: 10.1146/annurev-clinpsy-032511-143050. PubMed PMID: 22224835.
4. Jennett B. Thirty years of the vegetative state: clinical, ethical and legal problems. *Prog Brain Res*. 2005;150:537-43. Epub 2005/09/28. doi: 10.1016/S0079-6123(05)50037-2. PubMed PMID: 16186047.

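### H2 hypothesises a gain at least comparable to DBS, but the CRS-R analysis tests only for change from baseline, on a comparison of maxima that unequal assessment counts can inflate

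*Combined protocol and SAP*

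**What the plan says.** Among the main hypotheses at the end of the Background, H2 expects a gain in clinical measures of arousal and/or awareness "to an extent at least comparable to that demonstrated with neurosurgical thalamic stimulation procedures (i.e., DBS"). It refers to five earlier DBS publications. The text describes their results only qualitatively, with no scale, mean gain, response rate or margin.

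Aim 1 is more modest: "Assess the feasibility and preliminary efficacy of LIFUP thalamic stimulation, as measured by changes in clinical assessments measures of consciousness and behavioral responsiveness".

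Under Statistical Plan and Analysis, the CRS-R item is the only analysis of a clinical scale. Before the analysis, "the highest CRS-R prior-to and following LIFUP exposure will be calculated". Then "A matched samples T-test analysis will be performed". If a Shapiro-Wilk test detects non-normality, "a non-parametric Wilcoxon signed rank test will be used to compare Pre-LIFUP and Post-LIFUP scores for all patients". The extended Glasgow Outcome Scale is collected, but no analysis of it is planned.

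On timing, the Procedure section lists one baseline item per cycle, "Baseline clinical measures collection (25 min"), and one matching item after LIFUP. The Neurobehavioral Assessment Procedure section gives 25 minutes for one CRS-R and adds: "Responsiveness will also be assessed immediately following, as well as on the days following each LIFUP exposure". Neither section gives the number of assessments before or after LIFUP.

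**The concern.** H2 and the analysis answer different questions. H2 is comparative: is the gain at least about as large as with DBS? The analysis asks only whether scores rose. If the plan is followed exactly and the test is significant, the DBS clause is still untested, yet the result would be reported beside a hypothesis that contains it. Because the project presents LIFUP as a non-invasive alternative to DBS, that is a natural inference for a reader to draw.

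The narrower claim of an increase also needs care. There is no control group, so spontaneous recovery is part of the estimate. In addition, the maximum of several noisy scores tends to exceed the maximum of fewer. If assessments on later days make the post-LIFUP count larger than the pre-LIFUP count, the comparison favours LIFUP even when nothing has changed.

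**Working it through.** **1. H2 against the analysis**

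| Needed to support the DBS clause | In the documents |
|---|---|
| A DBS gain on a named scale | None; citations only |
| A margin defining comparable | None |
| A DBS, sham or other comparison group | None; all patients are analysed together, pre against post |
| A test or interval referred to the benchmark | None; paired t-test or Wilcoxon test |

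The null hypothesis is not written out. The standard null for both tests is no change, so rejecting it says only that the change differs from zero. The mixed-design ANCOVA in the DTI item concerns streamlines and defines no comparison group. There is no stated sample size, power or margin to reproduce.

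**2. Size of the effect of comparing maxima**

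Assumptions, because the documents give no figures: no LIFUP effect; normal within-patient errors with the same SD before and after; 10 to 20 patients; two-sided 5% level (none is stated for CRS-R).

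The expected maximum of k independent standard normal errors is 0 for k = 1, 0.564 for k = 2 and 0.846 for k = 3. The expected spurious change is the difference between the post and pre values:

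- 1 pre, 3 post: 0.846 − 0 = 0.85 within-patient SD
- 2 pre, 3 post: 0.846 − 0.564 = 0.28 within-patient SD
- equal counts: 0

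If the within-patient SD is 1 to 2 CRS-R points, this is 0.85 to 1.7 points with 1 and 3 scores, and 0.28 to 0.56 points with 2 and 3.

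The test favours LIFUP when mean(d) / (SD(d)/√n) exceeds t(0.975, n−1), where d is the patient's difference between maxima. Simulation under no effect gives:

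| Pre / post scores | Errors within period | n = 10 | n = 20 |
|---|---|---|---|
| Equal (1/1 or 3/3) | independent | 2.5% | 2.5% |
| 2 / 3 | independent | 11% | 19% |
| 2 / 3 | correlation 0.5 | 6% | 10% |
| 1 / 2 | independent | 23% | 46% |
| 1 / 3 | independent | 48% | 82% |
| 1 / 3 | correlation 0.5 | 25% | 48% |

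The percentages do not depend on the within-patient SD. Rounding scores to integers changes them little: with 1 and 3 scores, 43–79% at SD 1 and 47–81% at SD 2.

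**3. Limit on a Wilcoxon interval**

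The smallest exact two-sided signed rank p-value is 2/2^n. For n = 5 it is 2/32 = 0.0625; for n = 6 it is 2/64 = 0.031. With fewer than 6 patients, no 95% signed rank interval is available.

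**The case against.** The strongest reply is that H2 is a background hypothesis, that Aim 1 asks only for feasibility and preliminary efficacy in a small number of patients, and that the CRS-R item states its own question as pre against post. No success rule or decision rests on the DBS clause. This stands, and it limits the weight of the point: the planned test can run as written. It does not make the clause testable, and H2 is listed as a main hypothesis.

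A second reply is that the pre-LIFUP count may exceed one. Eligibility requires a CRS-R profile, which may be a separate assessment from the baseline or the same one, and the plan's reference to a maximum before LIFUP suggests several scores. The BOLD item also mentions patients with two exposures, and each cycle has its own baseline. This also stands. It is why the table includes 2 pre and 3 post, and why 48–82% should not be read as the trial's error rate.

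Three stronger readings are tempting but unsupported:

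- A reader might infer that the sponsor will choose a DBS figure after seeing the data. The absence of a benchmark leaves that possible; nothing says a numerical comparison is intended.
- A reader might infer that the CRS-R test is certainly biased. The count effect arises only if post assessments outnumber pre assessments, and the documents do not fix the counts.
- A reader might infer that patients in whom the beam is never aligned are dropped. The LIFU Procedure repeats positioning "until the beam trajectory from the center of the transducer is assessed to be in-line with the intended target" and does not say what follows if this fails. Reporting such cases would be useful, but its absence is not an error in this analysis.

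**Conclusion.** The mismatch holds and rests on the text alone: the plan contains nothing that could support the DBS clause of H2, and a significant CRS-R result would show at most an uncontrolled increase from baseline. The clause should be changed; the test itself need not be.

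The inflation from comparing maxima is conditional. The scheduling text makes a larger post-LIFUP count likely but does not establish it. Under the stated assumptions, the chance of a result favouring LIFUP with no effect runs from 2.5% with equal counts, through 11–19% (2 pre, 3 post), to 48–82% (1 pre, 3 post); within-period correlation of 0.5 roughly halves the unequal-count figures. Confidence is high for the mismatch. The size of the inflation depends on counts and error correlations that the documents do not give.

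**What to change.** 1. Limit H2 to: LIFUP thalamic stimulation is associated with an increase in clinical measures of arousal and/or awareness (CRS-R total score) from baseline. Give any DBS figures as descriptive context only. Keeping the clause would instead require a DBS benchmark on the CRS-R, a margin and a confidence-interval rule, all set in advance; the documents supply none of these.
2. Report the mean change with the t-test, or the Hodges-Lehmann estimate with the Wilcoxon test, with a 95% confidence interval, and list the individual changes. With fewer than 6 patients, the list replaces the signed rank interval. Tied integer scores make that interval's level approximate.
3. Report the number of CRS-R assessments before and after LIFUP for each patient, and state beside the estimate that it is uncontrolled and compares maxima.
4. Add a one-to-one sensitivity estimate: from the last CRS-R before the first LIFUP exposure to the CRS-R immediately after it. Both are already scheduled.

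A table of completed on-target sonications is an optional addition.

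The cost is one clause, one interval, one caveat, a column of counts and one extra estimate; no new patient data are needed. The one-to-one estimate removes the count effect but not spontaneous recovery, and it misses delayed effects. The headline claim becomes more modest.

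### Sedation short of deep is permitted and never recorded, so a fall in sedation after baseline would count as CRS-R change due to LIFUP

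*Combined protocol and SAP*

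**What the plan says.** Sedation is mentioned once, under Exclusion Criteria (all patients), as "deep sedation". No definition, scale, drug list or time point is given. The acute stratum is defined by "< 6 weeks since injury", together with a low coma score at injury, an abnormal CT and loss of consciousness for more than a day.

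Under Neurobehavioral Assessment Procedure, the pre-exposure side is described as "Baseline responsiveness will be assessed prior to LIFUP exposure", and the post-exposure side as "Responsiveness will also be assessed immediately following, as well as on the days following each LIFUP exposure". Neither the number of assessments nor the last post-exposure day is stated. The cycle under Procedure lists one 25-minute clinical slot before LIFUP and one after it, with a clinical EEG recording at the start and another at the end.

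The CRS-R item of Statistical Plan and Analysis states the comparison: "Maximum CRS-R score prior to LIFUP will be compared to the maximum CRS-R score following LIFUP". Scores are selected so that "the highest CRS-R prior-to and following LIFUP exposure will be calculated in order to best capture patients' maximal performance". The test is a paired t-test, or a Wilcoxon signed rank test if normality fails, over all patients together. No control group is described.

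**The concern.** A CRS-R total measures what the patient can show at the bedside, and a sedative can lower it. The plan lets lightly or moderately sedated patients in, takes post-LIFUP scores over several days, and does not ask what sedation was present at any of them. An acute patient who is lightly sedated at baseline, and whose sedation is reduced over the following days for ordinary clinical reasons, will tend to score higher later whether or not LIFUP does anything. With no control group, the analysis has no way to set that gain apart.

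This bears on Aim 1 and H2. H2 claims a gain at least comparable to that reported with deep brain stimulation, so the size of the change matters as well as its sign. The sample is described only as small, so a few such patients could move the mean. The problem differs from spontaneous recovery in one practical respect: sedation is a charted fact and can be examined without adding a control arm.

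**Working it through.** **Step 1: is there any rule elsewhere?**

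- Exclusion Criteria: deep sedation only.
- Neurobehavioral Assessment Procedure and Procedure: no sedation check or record.
- CRS-R analysis: scores chosen by height alone; no covariate.
- EEG and DTI analyses: a group analysis is named (a mixed-design ANCOVA for DTI), but sedation is not listed as a covariate.

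So lighter sedation is permitted, and nothing makes it comparable between assessments.

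**Step 2: what does a maximum-versus-maximum comparison do with sedation?** The plan gives no CRS-R effect size, SD or sample size, so it has no figure to reproduce. I use a simple two-state model with no LIFUP effect; all its values are assumptions.

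- c = CRS-R points lost when an assessment is made under sedation.
- q_pre, q_post = chance that any one assessment before or after LIFUP is made under sedation, independently.
- k_pre, k_post = number of assessments on each side.

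A maximum loses c only if every assessment on that side is sedated, so

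spurious gain = c × (q_pre^k_pre − q_post^k_post).

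| Chance of sedation, pre to post | Scores pre vs post | Calculation | Spurious gain |
|---|---|---|---|
| 0.50, constant | 1 vs 1 | 0.50 − 0.50 | 0 |
| 0.50, constant | 3 vs 3 | 0.125 − 0.125 | 0 |
| 0.50, constant | 1 vs 3 | 0.50 − 0.125 | 0.38c |
| 0.50 to 0.25 | 1 vs 1 | 0.50 − 0.25 | 0.25c |
| 0.50 to 0.25 | 3 vs 3 | 0.125 − 0.016 | 0.11c |
| 0.50 to 0.25 | 1 vs 3 | 0.50 − 0.016 | 0.48c |
| 0.75 to 0.25 | 1 vs 1 | 0.75 − 0.25 | 0.50c |
| 0.75 to 0.25 | 3 vs 3 | 0.422 − 0.016 | 0.41c |
| 0.75 to 0.25 | 1 vs 3 | 0.75 − 0.016 | 0.73c |
| 0.25 to 0.75 (rising) | 1 vs 1 | 0.25 − 0.75 | −0.50c |

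Three things follow. With constant sedation and equal counts there is no bias. With falling sedation, equal counts do not remove the bias. For a given pre-LIFUP side, more post than pre scores makes it larger.

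**Step 3: an illustration in CRS-R points.** Let f be the net fraction of patients less sedated at their best post score than at their best pre score (those less sedated minus those more sedated), and d the points this is worth. The bias in the mean change is f × d. With f from 10% to 40% and d from 2 to 4 points, all assumed:

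- low end: 0.10 × 2 = 0.2 points
- high end: 0.40 × 4 = 1.6 points

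In the 1 vs 1 case f equals q_pre − q_post, so the fall from 0.75 to 0.25 (f = 0.50) lies beyond this range and is a strong scenario. The fall from 0.50 to 0.25 (f = 0.25) gives 0.5 to 1.0 points for d of 2 to 4.

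**Step 4: which other outcomes are exposed?**

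- BOLD: the planned contrast sets 30-second LIFUP blocks against the pauses between them in the same run, after high-pass filtering at 0.01 Hz. A trend in sedation over days cannot create that contrast. Baseline and post-LIFUP fMRI are collected, but no analysis of that pair is specified.
- EEG: the two recordings belong to one cycle and no maximum is taken. The steps listed between them add up to 25 + 50 + 30 + 30 + 25 = 160 minutes, although the plan does not say that they fall on one day. EEG is exposed only if sedation changes between those two recordings.

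**The case against.** The premise is inferred. No section says that any enrolled patient is sedated or has sedation reduced; the acute window and the presence of the exclusion make it plausible, no more. The exclusion carries no time point, so reading it as an entry rule only is an interpretation. Chronic patients, who are pooled into the same test, may be little affected. All of this stands and limits how firmly the size can be stated. It does not supply the missing record.

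A reader might infer that taking the maximum makes the bias one-sided in favour of LIFUP. The plan does not support this: the maximum is taken on both sides, and the table shows zero gain under constant sedation with equal counts, and a negative one if sedation rises. The downward trend drives the bias; an excess of post-LIFUP scores adds to it.

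A reader might also infer that the fMRI result is biased, or that EEG and BOLD shift in a predicted direction. The within-run contrast is largely protected. H3 predicts only detectable change, and the EEG analysis asks only whether the spectrum alters.

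Finally, restricting scores by sedation after LIFUP conditions on a post-exposure variable, since a more responsive patient may be given less sedation. It also drops patients who have no comparable pair, who are the ones at issue, from a small sample. This is a sound reason not to make the restricted comparison the main analysis. It is not a reason to leave sedation unrecorded.

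**Conclusion.** The concern holds for the CRS-R comparison. As written, the plan permits sedation short of deep, does not record it, and would count a fall in sedation after baseline as change related to LIFUP, even with equal numbers of pre and post scores.

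The size cannot be derived from the documents. The range of 0.2 to 1.6 points rests wholly on assumed values of f and d and should not be read as an estimate; nor do the documents show that sedation will explain any observed change. What they show is that, without a sedation record, a positive pre/post result could not be separated from reduced sedation. For EEG the exposure is conditional on a change within a cycle; for the planned BOLD contrast it is small.

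**What to change.** - Extract from the chart the sedative drugs and the level of sedation in use at each CRS-R and each study EEG. A yes/no field is not enough to judge comparability; state in advance what counts as a comparable level.
- Keep the all-scores comparison of maxima as the main CRS-R analysis.
- Pre-specify a sensitivity analysis in which the pre and post maxima come only from assessments at a comparable sedation level within the patient. Report how many patients have no such pair.
- Report how many patients had lighter sedation at their best post-LIFUP score than at their best pre-LIFUP score, and how many had heavier.
- State that the CRS-R change will not be attributed to LIFUP if it is not seen in the sedation-comparable analysis. Judge this on the estimated change and its interval, because the smaller number of patients will weaken the test.
- For EEG, flag any cycle in which sedation differed between the two recordings.

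The cost is a modest amount of chart extraction and some SAP wording; no visit or procedure is added. The sensitivity analysis will have fewer patients and does not address spontaneous recovery. The change concerns recording and analysis only and alters no patient's sedation.
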